4.2 CONCOMITANT THERAPY, RESTRICTIONS, AND RESCUE TREATMENT

4.2.1 Rescue medication, emergency procedures, and additional treatment

An antidote against nintedanib is not available. Potential side effects of nintedanib have to be treated symptomatically.

Dose reduction (150 mg bid to 100 mg bid) or treatment interruption should be considered to manage adverse events. No further dose reduction is possible for patients on the 100 mg bid regimen. In case of adverse events observed at this dose, treatment interruption should be considered.

4.2.1.1 Management of diarrhoea

The guidelines for managing diarrhoea are the same as in the parent protocols.

4-6 extra stools or i.v. fluid intake < 24 hours with no effect on daily living activities

Patients should be treated according to local standard (e.g. loperamide or equivalent).

If the severity of diarrhoea persists for 8 or more consecutive days despite optimal care, nintedanib treatment should be discontinued or reduced until return to less than 4 extra stools per day. Drug interruption is limited however to a maximum of 4 weeks and patients may restart treatment with nintedanib at a reduced dose (during a dose modification visit, refer to [Section 6.2.4](#)).

Dose re-escalation is allowed at any time after the beginning of the reduced dose if medically justified.

In case of re-occurrence of diarrhoea for 8 or more consecutive days despite dose reduction and after optimal or prophylactic therapy, patients have to permanently stop nintedanib and perform an End of Treatment Visit as soon as possible and a Follow-up Visit 28 days after last drug intake (refer to the [Flow Chart](#) for visit procedures).

> 6 extra stools or incontinence or i.v. fluid intake ≥ 24 hours or hospitalisation or decrease in daily living activities

Nintedanib has to be interrupted until return to less than 4 extra stools per day and patients should be treated with optimal supportive care (e.g. loperamide or equivalent). Thereafter, patients may restart treatment with nintedanib at a reduced dose.

In case of re-occurrence of diarrhoea for 8 or more consecutive days despite dose reduction and after optimal or prophylactic therapy, patients have to permanently stop nintedanib and perform an End of Treatment Visit as soon as possible and a Follow-up Visit 28 days after last drug intake (refer to the Flow Chart for visit procedures).

Proprietary confidential information.

© 2017 Boehringer Ingelheim International GmbH or one or more of its affiliated companies. All rights reserved.

This document may not - in full or in part - be passed on, reproduced, published or otherwise used without prior written permission.

4.2.1.2 Management of liver enzyme elevation

The guidelines for managing liver enzyme elevations are the same as is in the parent protocols. The following procedures are based on the *FDA Guidance for Industry. Drug-Induced Liver Injury: Premarketing Clinical Evaluation (P09-12413)*.

ALT or AST > 1.5 fold ULN and < 3 fold ULN

- Continue as planned

ALT or AST \geq 3 fold ULN and < 5 fold ULN with no signs of severe liver damage

- Reduce to 100 mg bid or interrupt treatment (to be decided by investigator, based on individual risk assessment)
- Re-test ALT and AST, as well as alkaline phosphatase, total bilirubin and eosinophils within 48 to 72 hours, then at approximately 7 days, then at approximately 2 weeks, and assess signs of severe liver damage:
 - If ALT and AST < 3 fold ULN after 2 weeks, return to initial dose if reduced, restart at reduced dose if interrupted. Monitor lab (see above) every 2 weeks for at least 8 weeks.
 - If ALT and/or AST \geq 3 fold ULN after 2 weeks or any time thereafter, permanently discontinue study medication.

ALT or AST \geq 5 fold ULN and < 8 fold ULN with no signs of severe liver damage

- Interrupt treatment.
- Re-test ALT and AST, as well as alkaline phosphatase, total bilirubin and eosinophils within 48 to 72 hours, then at approximately 7 days, then at approximately 2 weeks, and assess signs of severe liver damage:
 - If AST and ALT < 3 fold ULN after 2 weeks, restart at reduced dose. Monitor lab (see above) every week for 4 weeks, then every 2 weeks for at least 8 weeks.
 - If AST and/or ALT \geq 3 fold ULN after 2 weeks or any time thereafter, permanently discontinue study medication.

ALT or AST \geq 8 fold ULN or signs of severe liver damage

- Permanently discontinue study medication.

Proprietary confidential information.

© 2017 Boehringer Ingelheim International GmbH or one or more of its affiliated companies. All rights reserved.

This document may not - in full or in part - be passed on, reproduced, published or otherwise used without prior written permission.

- Patients showing these lab abnormalities need to be followed up according to [Section 10.1.1](#) of this clinical trial protocol and the “DILI checklist” provided in ISF.

Signs of severe liver damage are defined as:

Increase of liver transaminases (ALT or AST \geq 3 fold ULN) and:

- appearance of fatigue, nausea, vomiting, right upper abdominal quadrant pain or tenderness, fever, rash, and/or eosinophilia ($>$ 5%); or
- Total bilirubin $>$ 1.5 fold ULN; or
- INR $>$ 1.5;

Please refer to [Section 10.1](#) for more detailed instructions.

Immediately refer to [Section 5.3.6.1](#) in case AST and/or ALT \geq 3 fold ULN is combined with total bilirubin \geq 2 fold ULN.

Initial assessment of liver enzyme elevation should be performed at the investigational site. Blood samples for additional monitoring may be collected at the investigational site, primary physician (GP or Pulmonologist) or external laboratory with specific study kits and sent to the central laboratory for analysis.

For patients continuing treatment with nintedanib within this trial after the database lock for the final analysis, the liver function monitoring is to be done locally in case of liver enzyme elevations.

4.2.1.3 Management of acute exacerbations

In case of acute exacerbation (refer to [Section 5.2](#)), all treatment options considered adequate by the investigator / caregiver are allowed. The patient may interrupt study treatment for up to 8 weeks if this is considered necessary (e.g., if short-term full anticoagulation is performed).

4.2.1.4 Management of other adverse events

Patients who develop an uncontrolled hypertension despite appropriate antihypertensive therapy should permanently discontinue study medication.

For AEs that are assessed drug related, a dose reduction or an interruption (of maximum 4 weeks) can be considered. Re-escalation is allowed at any time after start of dose reduction if medically justified.

Proprietary confidential information.

© 2017 Boehringer Ingelheim International GmbH or one or more of its affiliated companies. All rights reserved.

This document may not - in full or in part - be passed on, reproduced, published or otherwise used without prior written permission.

For non related AEs, drug interruption may occur for no longer than 12 weeks. Nintedanib should be re-started at the same dose as it was being taken before interruption.

Summary of allowed interruption periods:

- Acute IPF exacerbations: 8 weeks maximum interruption;
- Related AEs: 4 weeks maximum interruption, then dose reduction is recommended, then re-escalation to full dose (150 mg bid) is allowed at any time;
- Unrelated AEs: 12 weeks maximum interruption.

4.2.2 Restrictions

4.2.2.1 Restrictions regarding concomitant treatment

- Investigational therapy is not allowed during the entire study period and must not have been introduced in the interval between parent trial and enrolment into this extension trial.
- Nintedanib is an anti-fibrotic kinase inhibitor which has been shown to have anti-angiogenic properties. Inhibition of angiogenesis may increase susceptibility to bleeding. Therefore, concomitant anticoagulation, fibrinolysis or high-dose antiplatelet therapy is contra-indicated (refer to [Section 3.3.3](#) [4 weeks washout]). Patients who require fibrinolysis, full-dose therapeutic anticoagulation (e.g. vitamin K antagonists, dabigatran, heparin, hirudin), or high dose antiplatelet therapy are to be withdrawn. Prophylactic low dose heparin or heparin flush as needed for maintenance of an indwelling intravenous device (e.g. enoxaparin 4000 IU s.c. per day), as well as prophylactic use of antiplatelet therapy (e.g. acetyl salicylic acid up to 325 mg/d, or clopidogrel at 75 mg/d, or equivalent doses of other antiplatelet therapy) should be allowed.
- The concomitant administration of nintedanib with any drugs which are likely to increase gastrointestinal events such as diarrhoea, nausea, vomiting, is discouraged.
- Washout of bronchodilators must be observed before spirometry: 24 hours for long acting and 8 hours for short acting bronchodilators, if applicable.

4.2.2.2 Restrictions on diet and life style

No restrictions on diet or life style.

Proprietary confidential information.

© 2017 Boehringer Ingelheim International GmbH or one or more of its affiliated companies. All rights reserved.

This document may not - in full or in part - be passed on, reproduced, published or otherwise used without prior written permission.

4.3 TREATMENT COMPLIANCE

Study medication will be dispensed to the patient at the study site by responsible site personnel. Details regarding dispensing of the study medication to each participating patient, including patient identification, the amount of study drug dispensed, the date the drug was dispensed, and the number of capsules returned to the site will be recorded in the drug accountability form.

Patients will be instructed to bring all study medication to the clinic at each visit (except Visits 3 and 5). The investigator will be responsible for the assessment of patient compliance and will be encouraged to counsel patients on the importance of taking study medication as directed at each visit.

Study medication will be counted by the investigator (or designated site personnel) and compliance will be calculated in a worksheet, which must be kept as a source document.

Compliance will be calculated according to the formula: Compliance (%) = Number of capsules actually taken since last count \times 100 / Number of capsules which should have been taken in the same period. Compliance to nintedanib should be between 80% and 120%.

Patients should not be discontinued for lack of compliance without prior discussion with the clinical monitor.

Proprietary confidential information.

© 2017 Boehringer Ingelheim International GmbH or one or more of its affiliated companies. All rights reserved.

This document may not - in full or in part - be passed on, reproduced, published or otherwise used without prior written permission.

5. VARIABLES AND THEIR ASSESSMENT

5.1 TRIAL ENDPOINTS

5.1.1 Primary Endpoint

The primary endpoint is the incidence (number and % of patients) of overall adverse events over the course of the study, including incidence (number and % of patients) of serious adverse events; adverse events leading to discontinuation and fatal adverse events.

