7.3.1 Primary endpoint analyses

The primary objective of the study is to assess the safety of nintedanib, so please refer to [Section 7.3.4](#). Number of patients and % will be presented over the extension trial by

Proprietary confidential information.

[figure not shown]
© 2017 Boehringer Ingelheim International GmbH or one or more of its affiliated companies. All rights reserved.

This document may not - in full or in part - be passed on, reproduced, published or otherwise used without prior written permission.

category for adverse events overall; serious adverse events; adverse events leading to treatment discontinuation and fatal adverse events.

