## **7. PLANNED ANALYSIS**

For End-Of-Text (EoT) tables, the set of summary statistics is: N / Mean / SD / Min / Median / Max.

Tabulations of frequencies for categorical data will include all possible categories and will display the number of observations in a category as well as the percentage (%) relative to the respective treatment group (unless otherwise specified, all patients in the respective patient set whether they have non-missing values or not). Percentages will be rounded to one decimal place. The category missing will be displayed only if there are actually missing values.

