## **7.7 EXTENT OF EXPOSURE**

The data will be analysed on the Treated Set.

A summary table showing the duration on treatment (both mean and frequency in classes, see [Section 5.4.3](#)) will be performed.

A table displaying the disposition of patients and the conclusion of patients' participation, and a table displaying the primary reason for non-inclusion will be provided.

The proportion of patients on each dose actually taken at visit 2 will be displayed according to:

- randomized treatment group in parent trial (by parent trial and both combined)
- the dose actually taken at the end of parent trial (by parent trial and both combined)
- the dose actually taken at the end of 1199.33 extension trial

A summary of treatment interruption will be performed including number of patients with at least one interruption, number and reason of interruptions, as well as time to first treatment interruption in 1199.33. A similar summary will be performed for dose change.

Besides, a summary table showing the duration on actual treatment dose (both mean and frequency in classes, see [Section 5.4.3](#)) and off-treatment duration will be performed by randomized group of the parent trial. This will take into account the actual dose following dose reductions or increases.

Kaplan-Meier plots of time to permanent treatment discontinuation will be drawn by randomised treatment in parent trial and overall. Similarly, Kaplan-Meier plots will be performed for time to first dose reduction and for time to first treatment interruption by randomised treatment in parent trial and overall. No statistical tests will be performed.

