### **7.8.1 Adverse events**

Unless otherwise specified, the analyses of adverse events will be descriptive in nature and will be based on BI standards (2). All analyses of AEs will be based on the number of patients with AEs and NOT on the number of AEs.

Furthermore, for analysis of AE attributes such as duration, severity, etc. multiple AE occurrence data on the CRF, will be collapsed into AE episodes provided that all of the following applies:

- The same MedDRA lowest level term was reported for the occurrences
- The occurrences were time-overlapping or time-adjacent (time-adjacency of 2 occurrences is given if the second occurrence started on the same day or on the day after the end of the first occurrence)
- Treatment did not change between the onset of the occurrences OR treatment changed between the onset of the occurrences, but no deterioration was observed for the later occurrence

The analysis of adverse events will be based on the concept of treatment emergent adverse events. That means that all adverse events occurring between first drug intake in 1199.33 until 28 days after last drug intake in 1199.33 will be assigned to the on-treatment period and described according to randomised treatment in parent trial. All adverse events occurring before first drug intake in 1199.33 will be assigned to 'screening' and all adverse events occurring after last drug intake + 28 days will be assigned to 'post-treatment', 'post-study' or 'follow-up' (for listings only). Some queries will be edited in case some adverse events are incorrectly reported in 1199.33 instead of parent trial, in order to report these in parent trial instead (before parent trial DBL). Also, all adverse events occurring between the start of an interruption and the end of interruption will be assigned to 'off-treatment' period in the listings. For details on the treatment definition, see [Section 6.1](#).

According to ICH E3 (3), AEs classified as 'other significant' will include those non-serious and non-significant adverse events with

- (i) 'action taken = discontinuation' or 'action taken = reduced', or
- (ii) marked haematological and other lab abnormalities or lead to significant concomitant therapy as identified by the Clinical Monitor/Investigator at a Blinded Report Planning Meeting.

An overall summary of adverse events will be presented.

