The frequency of patients with adverse events will be summarised by randomised treatment in parent trial, primary system organ class and preferred term. Separate tables will be provided for patients with other significant adverse events according to ICH E3 (3), for

patients with serious adverse events, for patients with adverse events occurring with an incidence in preferred term greater than 5% (in at least one treatment arm), for patients with protocol specified significant adverse events (as ticked in the AE page of the CRF), for patients with related adverse events, for patients with adverse events leading to dose reduction and for patients with adverse events leading to treatment discontinuation.

The system organ classes will be sorted according to the standard sort order specified by EMA, preferred terms will be sorted by descending frequency over the total column (within system organ class).

Specific tables will be created in order to describe selected adverse events of particular note, such as diarrhoea events:

- Display of the diarrhoea specific page of the CRF
- Summary of diarrhoea events including time to onset, number and duration of episodes
- Summary of diarrhoea adverse events including seriousness, clinical consequences (dose -reduction, drug discontinuation or drug interruption) and outcome
- Kaplan-Meier plots of time to first diarrhoea event, by randomised treatment in parent trial and overall

Specific summary tables including seriousness, clinical consequences and outcome will also be presented to describe the following adverse events of particular note: nausea, vomiting, dehydration and weight decrease adverse events. Depending on the number of patients having such adverse events, summary tables including time to onset, number of episodes and duration together with Kaplan-Meier plots of time to first event, by randomised treatment in parent trial and overall, may also be produced with and without a y-axis cut-off at 70%.

Topics or syndromes that are medically relevant to the clinical development program are specified in [Table 7.8.1: 1](#). The frequency of patients with AEs within these topics or syndromes will be summarised by treatment, topic or syndrome and preferred term. A separate table will be provided for patients with serious AEs (SAEs), by treatment, topic or syndrome and preferred term.

Table 7.8.1:1 Aggregated adverse events by topic or syndrome

Organ system	Topic or Syndrome	Term selection

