## 10. HISTORY TABLE

This is a revised TSAP including the following modifications to the final TSAP

Table 10: 1 History table

Version	Date (DD-MMM-YY)	Author	Sections changed	Brief description of change
Final	14-June-13	[REDACTED]	None	This is the final TSAP without any modification
Revised	29-September-15	[REDACTED]	4	As the protocol has been revised, the term "On trial survival" has already been changed into "Time to death"
			5.2.2	In accordance with new SOP, endpoints are now classified as further endpoints and not as secondary endpoints anymore.
			[REDACTED]	[REDACTED]
			[REDACTED]	[REDACTED]
			[REDACTED]	[REDACTED]
			[REDACTED]	[REDACTED]
			6.2	Precision added for IPV A2.1
			6.6	A reference to the CTP has been added for the handling of missing data.
			7.5.2	In accordance with new SOP, endpoints are now classified as further endpoints and not as secondary endpoints anymore.
			[REDACTED]	[REDACTED]
			7.7, 7.8.1	Precision that KM plots will also be performed overall groups and with 70% cut-off for y-axis for AEs of particular note
			[REDACTED]	[REDACTED]
			General	Reference section numbers have been updated or removed due to new classification of endpoints and for consistency purposes with revised CTP based on Global amendment 2.

Table 10: 1 History table (cont'd)

Revised	19-September-16	[REDACTED]	6.3	The definition of the Treated Set has been updated in order to specify that the Treated Set only includes patients from parent trials 1199.32/34 (and not transitioned patients from study 1199.35).
				[REDACTED]
Revised	25-Jul-17	[REDACTED]	7.2	The definition of baseline therapies was clarified. A summary of post-study drug discontinuation therapies has been added in order to display the proportion of patients having taken commercial nintedanib after trial drug discontinuation.
			7.8	Some specific AE tables by Topic or syndrome were added, as judged medically relevant for the project.
				[REDACTED]
				[REDACTED]

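### The primary adverse event categories and the Table 7.8.1:1 topics are summarised only as n (%) of patients over variable exposure, with no time at risk to first event in the visible text

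*Protocol*

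**What the plan says.** **Primary endpoint.** Protocol 5.1.1: "The primary endpoint is the incidence (number and % of patients) of overall adverse events over the course of the study". The endpoint includes serious events, events leading to discontinuation and fatal events. Protocol 7.3.1 repeats the measure: "Number of patients and % will be presented over the extension trial by" category.

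**How events are counted.** SAP 7.8.1: "All analyses of AEs will be based on the number of patients with AEs and NOT on the number of AEs". The on-treatment period is one window, from first intake in 1199.33 to 28 days after last intake. Under SAP 7, tabulations "will display the number of observations in a category as well as the percentage (%) relative to the respective treatment group". Unless otherwise specified, that means every patient in the set.

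**Topics.** For Table 7.8.1:1, "The frequency of patients with AEs within these topics or syndromes will be summarised by treatment, topic or syndrome and preferred term", with a second table for serious events. The history table records for July 2017: "Some specific AE tables by Topic or syndrome were added, as judged medically relevant for the project".

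**Exposure.** The protocol synopsis says treatment duration will vary by patient and that the trial lasts about 6½ years. Protocol 7.4 has the Section 7.3 analyses presented at each of three data cuts.

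**Time-aware displays that are planned:**
- Kaplan-Meier for diarrhoea, and optionally for nausea, vomiting, dehydration and weight decrease (SAP 7.8.1).
- Kaplan-Meier for laboratory liver enzyme elevation, if there are enough events (SAP 7.8.2).
- SAP 7.7: "Kaplan-Meier plots of time to permanent treatment discontinuation will be drawn by randomised treatment in parent trial and overall". The same is planned for dose reduction and interruption, with tables of duration on treatment.
- Censoring rules for death and first acute exacerbation (SAP Table 6.6.1:1).

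**The concern.** The sole objective is long-term safety. When follow-up differs between patients, the percentage ever having an event depends on the event rate and on how long patients were watched. It can rise from one data cut to the next, or differ between the two parent-trial groups, while the rate is unchanged.

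Exposure can also end for reasons unrelated to safety. Protocol 3.3.4.2 lists marketing authorisation as a ground for stopping the trial or a site, and the rationale for Amendment 3 gives access to nintedanib outside the trial as the reason for ending it in most participating countries.

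The second weakness is timing. One percentage over the whole window cannot show whether bleeding or thromboembolic events, for example, cluster early, stay constant or become more frequent with longer treatment. A long-term extension is well placed to answer that question. It also matters because former placebo patients start nintedanib for the first time here, while the others continue it.

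**Working it through.** There is no planned figure to reproduce: Protocol 7.2 foresees no formal inference and 7.7 gives no sample size calculation. The check has a textual part and an illustrative part.

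**1. Do the planned time-aware displays reach the categories in question?**

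| Planned display | Nearest category here | Why it does not cover it |
|---|---|---|
| Time to death (SAP Table 6.6.1:1) | Fatal adverse events | Runs to last contact; the adverse event window stops 28 days after last intake |
| Time to permanent discontinuation (SAP 7.7) | Events leading to discontinuation | Not restricted to adverse events |
| Time to liver enzyme elevation (SAP 7.8.2) | Liver enzyme and bilirubin topic | Laboratory finding, conditional on numbers; the topic is defined by MedDRA queries |
| Kaplan-Meier for diarrhoea, nausea, vomiting, dehydration, weight decrease (SAP 7.8.1) | None | Not Table 7.8.1:1 topics |
| Duration on treatment (SAP 7.7) | All | Gives total exposure, not time to first event |

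No visible text gives time at risk for overall, serious, discontinuation-related or fatal adverse events, or for the topics.

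**2. How far can a crude percentage move at a constant rate?** The documents give no exposure distribution for the extension, so the rates r and exposures T are assumptions, with no dropout. Crude incidence = 1 − exp(−rT).

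| Assumed r per 100 patient-years | 1 year | 3 years | 5 years |
|---|---|---|---|
| 2 | 2.0% | 5.8% | 9.5% |
| 5 | 4.9% | 13.9% | 22.1% |
| 10 | 9.5% | 25.9% | 39.3% |

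The same applies between groups. If time under observation is exponential with mean m, crude incidence = r/(r + 1/m). With r = 0.05 per year, m = 1.5 years gives 0.05/(0.05 + 0.667) = 7.0%, and m = 3 years gives 0.05/(0.05 + 0.333) = 13.0%.

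**3. Can the percentage show a time pattern?** Take three sets of yearly hazards over 3 years, each summing to 0.15, so crude = 1 − exp(−0.15) = 13.9% in each. Time at risk per patient is the sum over years of S × (1 − exp(−h))/h, where h is the year's hazard and S is the proportion event-free at its start. The pooled rate is crude incidence divided by time at risk.

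| Pattern (per 100 patient-years, years 1/2/3) | Crude at 3 years | Years at risk per patient | Pooled rate |
|---|---|---|---|
| Early: 10/2.5/2.5 | 13.9% | 2.717 | 5.1 |
| Flat: 5/5/5 | 13.9% | 2.786 | 5.0 |
| Late: 2.5/2.5/10 | 13.9% | 2.856 | 4.9 |

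The crude percentage cannot separate these patterns, and the pooled rate hardly does. A display by interval is therefore needed as well as a rate.

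**4. Would the rates be precise enough to use?** With the planned 750 patients (Protocol 3.1) and an assumed r = 0.05, time at risk = 750 × (1 − exp(−0.05T))/0.05. The exact Poisson 95% CI is per 100 patient-years.

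| T | Events | Patient-years | 95% CI |
|---|---|---|---|
| 1 year | 37 | 731.6 | 3.6 to 7.0 |
| 3 years | 104 | 2089.4 | 4.1 to 6.0 |
| 5 years | 166 | 3318.0 | 4.3 to 5.8 |

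**The case against.** **Unseen text.** Protocol 7.3.4 points to Sections 7.3.1 and 7.3.3, and 7.3.3 is not visible. Neither are SAP 5.4 and 9.2, nor the sponsor adverse event standard on which SAP 7.8.1 relies. Any of these could require exposure-adjusted rates. This stands, and it is why absence is claimed for the visible text only and why the first step is to check.

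**A reader can approximate a rate.** SAP 7.7 tabulates mean duration, so N × mean gives total patient-years and n can be divided by it. On the 3-year assumptions this gives 5.82/3 = 1.94 against a true 2.0, 13.93/3 = 4.64 against 5.0, and 25.92/3 = 8.64 against 10 per 100 patient-years. That is close for uncommon topics and less so for common events. It omits the 28-day tail and shows nothing about timing.

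**Topics and data cuts.** Topic tables added in July 2017 may serve the final cut only. That is plausible: the parent-trial reports date from April 2014 and entry was limited to 12 weeks after parent Visit 9, so the 48-week cut probably came earlier. The cut-to-cut argument then applies to the four primary categories, and the timing argument still applies to the topics.

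**Key expected risks are already covered.** Gastrointestinal events, weight decrease and liver enzymes do have time-aware displays, some of them conditional. That narrows the gap but leaves the primary categories and the topics outside it.

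**The figures are hypothetical.** They are. The 5-year, no-dropout column in particular fits poorly with the 2–3 year life expectancy in Protocol 1.1. The dependence on exposure is already visible between 1 and 3 years.

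**Conclusion.** The point holds for the visible text. The four primary categories and the Table 7.8.1:1 topics are planned as numbers and percentages of patients over variable exposure, and the planned time-aware displays cover other items. On assumed constant rates of 2 to 10 per 100 patient-years, the crude percentage rises roughly threefold between 1 and 3 years (2.0% to 5.8%, up to 9.5% to 25.9%) with no change in risk. Opposite time patterns can produce the same 13.9%.

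These sizes rest on assumed rates, assumed exposure and no dropout. The consequence is for interpretation: all analyses are descriptive, and SAP 6.3 makes the total column the main interest, so no test is invalidated. It should be fixed, because the gap bears directly on the long-term safety objective and the remedy is cheap. Confidence is medium because relevant text is not visible.

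**What to change.** First confirm whether the sponsor adverse event standard, Protocol 7.3.3 or a SAP section not visible here already requires exposure-adjusted rates. If one does, state this in SAP 7.8.1, since these categories are the primary endpoint. If none does, keep the n (%) tables and make three additions.

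1. For serious events, events leading to discontinuation, fatal events and each Table 7.8.1:1 topic, add to SAP 7.8.1:

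> *Number of patients with a first event per 100 patient-years at risk, time at risk running from first 1199.33 intake to the first event or last intake + 28 days (or the cut-off date if earlier), with exact Poisson 95% CI, by parent-trial group and total.*

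2. For the same items, add either these rates by exposure interval (year 1, 2, 3 and later) with numbers at risk, or cumulative incidence with death as a competing event. For fatal events, death is the event itself. Death cannot be ignored given the life expectancy the protocol states.

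3. For overall adverse events, use the interval display only. Diarrhoea alone affected 61.5% and 63.2% of nintedanib patients in the 52-week parent trials (Protocol 1.2), so most first events are likely to come early and a pooled rate would add little.

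The cost is SAP wording, some programming and extra tables. Onset and intake dates are already collected, and Table 6.6.1:1 already uses last intake + 28 days for adverse events of particular note. No new patients, visits or procedures are needed.
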